6 DESIGN OF THE CLINICAL INVESTIGATION

6.1 General

This will be a prospective multi-center, multi-national comparative non-blinded clinical investigation. Each subject will undergo back-to-back tandem colonoscopies with the Aer-O-Scope Colonoscope System and a conventional colonoscope (for a list of scopes to be used, see Appendix 2) since this is a tandem colonoscopy study, each subject will serve as their own control. The 1st procedure will be randomized, half to Aer-O-Scope Colonoscope System and half to conventional colonoscope. The same investigator will perform both procedures on each subject. All pathologies found will be either removed or tattooed. Unmarked pathologies found on second pass will represent those missed during the 1st pass, thus making the subject and the control one and the same. Tattooed pathologies that can be removed endoscopically will be removed in an additional colonoscopy. This may occur if a large polyp cannot be removed for any reason with the Aer-O-Scope, but can be removed with conventional colonoscopy.

Subjects will be randomized in blocks of twenty (20) for either Aer-O-Scope or conventional colonoscopy as the first procedure. Physicians will be notified of the procedural order immediately prior to first colonoscopy. Up to the first ten (10) cases for each physician (system operation training cases) will all begin with the Aer-O-Scope colonoscopy as the first procedure.

The primary endpoint of AMR was chosen as this measure appears to be related to the performance of colonoscopy and reduction in colorectal cancer incidence. During the course of the last decade, several major visualizations studies have been performed and it has become common practice to use the “second-pass” method for measuring colonoscopy visualization methods^{iii,iv}. In the “second-pass” method, during the course of the first colonoscopy, all visualized lesions are removed (or tattooed in the event that they cannot be removed for any reason.). Any unmarked abnormalities discovered during the second pass colonoscopy are considered to be missed pathologies for the first pass colonoscopy.

All endpoints related to timing will be measured using a stopwatch and overall time stamp from the Aer-O-Scope or conventional colonoscope. Time to perform therapeutic interventions with Aer-O-Scope as well as a description of said interventions will also be recorded. The same instruments will be used to measure all procedures and will be calibrated as dictated by the manufacturer.

All equipment used during the course of this clinical investigation will undergo calibration and testing as per the manufacturing instructions. The Aer-O-Scope Colonoscope System has an automated calibration system and diagnostic test that run daily. Conventional colonoscopes will be maintained as per hospital/manufacturer protocol.

Recruited subjects who are withdrawn as a result of poor bowel prep or any other medical determination leading to the inability to undergo colonoscopy and/or tandem colonoscopy will be

Clinical Investigational Plan			
Protocol ID	934CLD	Sponsor	GI View Ltd.
Revision	03	Investigational Device	Aer-O-Scope® Colonoscope System

replaced. A poor prep is defined as having a score of score of 0 or 1 in the Boston Bowel Preparation Scale (BBPS). The BBPS scores are as follows:

- 0** = Unprepared colon segment with mucosa not seen due to solid stool that cannot be cleared.
- 1** = Portion of mucosa of the colon segment seen, but other areas of the colon segment not well seen due to staining, residual stool and/or opaque liquid.
- 2** = Minor amount of residual staining, small fragments of stool and/or opaque liquid, but mucosa of colon segment seen well.
- 3** = Entire mucosa of colon segment seen well with no residual staining, small fragments of stool or opaque liquid.

Any subject withdrawn as a result of physician discretion due to concomitant medical issues will be withdrawn prior to the actual colonoscopic procedures. Patients with a large polyp (>20mm) removed during the first pass with a conventional colonoscope will be withdrawn. Patients who receive treatment during the first pass with clips (no other option available) will be withdrawn. Coagulation therapy should be performed either with Argon Plasma Coagulation (APC) or another cautery tool or contact thermal device as per clinical protocol. For the purpose of this clinical investigation, clips should not be used unless there is no alternative. Patients treated with clips *prior to their final pass colonoscopy*, will be withdrawn from the investigation. Physicians may also withdraw any patient due to medical causes if deemed appropriate, including patients that have undergone at least one (1) procedure.

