Number of Subjects	
Three hundred and 10 (310):
 
Up to ten (10) training cases per investigator per site) plus eighty (80) study subjects per site (between one hundred (100) and one hundred and ten (110)subjects per site (dependent on the number of investigators including training cases)
 
Each site will have three (3) study cohorts:
 
 ✓ Training cohort (up to the first 10 cases per investigator) Aer-O-Scope colonoscopy followed by conventional colonoscopy (not part of the statistical evaluation for visualization) ✓ Aer-O-Scope colonoscopy followed by conventional colonoscopy ✓ Conventional colonoscopy followed by Aer-O-Scope colonoscopy
Study Duration	One (1) Year

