Medical Procedure	
The Aer-O-Scope Disposable Scanner like any conventional colonoscope is inserted into the rectum and then maneuvered to the cecum. The Aer-O-Scope has an incorporated propulsion system to advance the optical imaging head through the colon. The propulsion system utilizes soft pliable balloons and CO₂ gas to gently propel the optical imaging head inwards on intubation and outwards upon retraction. The operator gently eases the multi-luminal cable inward towards the cecum during the insertion phase and gently pulls the cable during retraction scan phase both while steering the optical imaging head with the ergonomic joystick.
 
If pathology of any type is detected during the procedure, a standard therapeutic accessory (at least 230cm in length and ≤1.8mm in diameter) is inserted through one of the Aer-O-Scope two (2) working channels (2.1mm diameter each) and the polyp is removed or biopsied. In the event that the pathology cannot be removed due to size, shape and/or location, the area adjacent to the pathology is tattooed to mark for later therapeutic intervention.
 
In this study, subjects will undergo tandem colonoscopy with the Aer-O-Scope Colonoscope System and a conventional colonoscope (see Appendix 2: Conventional Colonoscopes Used in this Investigation). Subjects will be randomized in blocks to begin either with the Aer-O-Scope Colonoscope System or with the conventional colonoscope. The same endoscopist will perform both procedures. Because the physicians will see which device they are using to perform the colonoscopies, blinding will not be possible.
 
Each subject will undergo colonoscopy in tandem with each device. All pathologies will be removed (or tattooed) during the procedures.
 
Data will be documented on Case Report Forms (973CLD). Data related to adenomas will be retrieved from histology reports.

Clinical Investigational Plan			
Protocol ID	934CLD	Sponsor	GI View Ltd.
Revision	03	Investigational Device	Aer-O-Scope® Colonoscope System

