9 AMENDMENTS TO THE CIP

Amendments	
All subsequent amendments to the CIP must also be agreed and approved by the sponsor, the coordinating investigator and all principal investigators.
 
The Sponsor / CRO will ensure that
 
9.1 Amendments to the Clinical Investigation Plan are documented, using form 698CLP 'CIP Amendment and Revision Sheet'
 
9.2 approval is documented, using form 693CLP 'Clinical Investigation Document Approval Log'
 
9.3 the amended CIP is sent to all investigators and the IRB / EC after approval

-------------------	---

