16 EARLY TERMINATION OR SUSPENSION OF THE CLINICAL INVESTIGATION

Suspension or Premature Termination	
Grounds for suspension or premature termination of the clinical investigation include but are not limited to:
 
Non compliance of the investigational site personnel to the CIP and or investigational procedures
 
Severe Adverse Events that demonstrate danger to the patient population
 
Unethical performance on the part of any of the investigators
 
Device Adverse Effects that demonstrate danger to the patient population or severe flaw in investigational device design
 
Failed audit of investigation with serious flaws to study design,

--	--

Clinical Investigational Plan			
Protocol ID	934CLD	Sponsor	GI View Ltd.
Revision	03	Investigational Device	Aer-O-Scope® Colonoscope System

	
performance or outcomes
 
Business/Financial issues that cannot be resolved
 
Other unforeseen events that give the PI/Sponsor reasonable doubts to the safety and/or performance of the system which will be referred to the Data Safety Monitoring Committee for review prior to determination of suspension or termination.

Blinding/Masking Technique	This clinical investigation does not include any blinding or masking.
Follow-Up	Patients will be followed up 24-48 hours post procedure via telephone by the clinical coordinator at each site. Patients who undergo therapeutic interventions will only be terminated from the study upon receiving the histology results.

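### One fixed block size of 20, printed in the plan that operators hold, lets anyone who follows a whole block deduce its 20th order and, on average, 1.8 orders per block.

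*Combined protocol and SAP*

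**What the plan says.** - **Blocking.** Section 6.1: "Subjects will be randomized in blocks of twenty (20) for either Aer-O-Scope or conventional colonoscopy as the first procedure". The same section gives the split: "The 1st procedure will be randomized, half to Aer-O-Scope Colonoscope System and half to conventional colonoscope". It does not say whether blocks are formed by site, by investigator or across the study, nor that each block is 10:10.
- **Concealment step.** Section 6.1: "Physicians will be notified of the procedural order immediately prior to first colonoscopy". The plan does not say who generates or holds the list.
- **Blinding.** Section 16: "This clinical investigation does not include any blinding or masking". Section 2 (Medical Procedure) adds: "Because the physicians will see which device they are using to perform the colonoscopies, blinding will not be possible", and "The same endoscopist will perform both procedures". Each operator therefore knows the order of every case that he or she performs.
- **Who holds the plan.** Section 9 requires all principal investigators to approve amendments, and says: "the amended CIP is sent to all investigators and the IRB / EC after approval".
- **Numbers.** The synopsis (Section 1.5) gives "eighty (80) study subjects per site", Section 6.2 gives three sites, and Section 7 gives 240 patients excluding training cases.
- **Exits and replacement.** Section 6.1 lets the physician withdraw a subject before the procedures because of concomitant medical issues. It replaces subjects who cannot undergo colonoscopy or the tandem examination for poor preparation or another medical reason. Section 6.4 logs those who consent but are never scoped as screen failures and takes them off the roster. The plan does not say whether a replaced subject's order is used again.

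**The concern.** The primary comparison is between the two order cohorts. Section 6.1 calls each subject their own control, but the AMR of each cohort comes from different subjects, so it depends on who enters which order. In an unblinded study where one operator does both passes, concealed allocation is one of the few protections against a difference in case mix.

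Late disclosure protects concealment only if the next order cannot be worked out beforehand. Here past orders are visible to the person performing the cases, and the block size is a single published number. Once ten subjects in a 10:10 block have started with one device, every remaining order in that block is fixed. Someone who knows or suspects the next order could let it influence whether a particular subject goes ahead, is withdrawn before scoping, or is replaced.

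**Working it through.** The plan gives no figure for predictability. Its 240 is used only to count blocks and is not disputed: 3 sites × 80 = 240, and 240/20 = 12 blocks, or four per site if blocked by site.

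**Assumptions that the plan does not state:** 10:10 within each block, blocking by site, and an observer who sees every order in the block and knows where it starts.

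**1. Orders that become certain.** In a block of 2m with m = 10, the last k or more orders are certain when they are all the same. The probability is 2·C(20−k, 10)/C(20, 10), with C(20, 10) = 184,756.

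| k | Calculation | Share of blocks |
|---|---|---|
| 1 | 2 × 92,378/184,756 | 100% |
| 2 | 2 × 43,758/184,756 | 47.4% |
| 3 | 2 × 19,448/184,756 | 21.1% |
| 4 | 2 × 8,008/184,756 | 8.7% |

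The mean is 2m/(m+1) = 20/11 = 1.82 per block, or 9.1% of allocations. Over 12 blocks this is 12 × 1.82 = 21.8, about 22 of 240.

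**2. Guessing the remaining orders.** Always guessing the order that lags so far, the expected number correct per block is m + (2^(2m)/C(2m, m) − 1)/2 = 10 + (1,048,576/184,756 − 1)/2 = 10 + (5.675 − 1)/2 = 12.34. That is 12.34/20 = 61.7%, or about 148 of 240, against 120 by chance. By position, the hit rate is 50% at the first subject, 58.6% at the 10th and 11th, 66.7% at the 16th and 17th, 73.7% at the 18th and 19th, and 100% at the 20th.

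**3. An operator who sees only part of a block.** Section 7 allows 20–30 training subjects per site and the synopsis up to 10 per investigator, which suggests two or three operators per site. In a simulation where the operator counts only his or her own share of each block, the hit rate is about 54.9% (half) or 53.6% (one third). The 20th slot is then no longer bound to be certain.

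**4. What varying the block size changes.** Take sizes 16, 20, 20 and 24 in random sequence, which sum to 80.
- Simulated lag-guessing with the sizes undisclosed is right about 61.6% of the time.
- If the sizes were known, the formula in step 2 gives 10.05, 12.34, 12.34 and 14.60, so 49.33/80 = 61.7%.
- Other undisclosed mixes over 80 subjects give 62.1% (sizes 8 to 24), 62.5% (10 to 20) and 67.8% (4, 6 and 8).
- A fixed block of 4 gives 70.8%.

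The average guess rate therefore hardly moves with long varying blocks, and it rises with short ones. What disappears is the slot that an observer can count to and know. One such slot survives if the sizes are known to total exactly 80: the 80th order at each site.

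**The case against.** The strongest reply is that the weakness is small and the route to bias is not documented. Twenty is already a long block and is less guessable than the shorter ones above. The order is disclosed late, and consent normally comes before bowel preparation (Section 6.3), so it cannot usually depend on a disclosed order. Several operators may share a site, no shared log of orders is described, and replacements blur the count. How visible a subject's adenomas are is not known before the scope. The same unblinded endoscopist performing both passes is a more direct source of bias, and better concealment does not touch it.

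Most of this stands, and it limits what may be inferred:
- A reader might infer that the last several orders of every block are certain. Only the 20th is; two or more are certain in fewer than half of blocks.
- A reader might take 22 and 148 of 240 as expected values. They are ceilings under the listed assumptions.
- A reader might infer that operators pick which consented subject goes next. The plan does not say so, and Section 8 gives the coordination of hospital visits to the site coordinator.
- A reader might infer that the AMR comparison is biased. Nothing in the documents shows that, or gives a size for it.

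What does not stand is the idea that late disclosure closes the gap. It does not prevent counting. Consent before preparation does not close it either, because withdrawal, screen failure and replacement come after consent, and Section 6.3 also permits consent on the procedure day.

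**Conclusion.** The point holds as a concealment weakness of minor to moderate weight. A single published block size gives a full observer one certain order in every block and 1.8 on average. With blocks of 10:10 by site and sight of every order, the ceiling is about 22 of 240 certain orders and 61.7% correct guesses. With sight of half or a third of each block, the hit rate is only about 4 to 5 percentage points above chance. Selection is possible through the exits before scoping, but whether it would occur, and what it would do to AMR, cannot be worked out from the documents. The case for acting rests on the low cost and on the primary comparison being between order cohorts.

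The blocking sentence could also be taken to mean that whole groups of 20 receive one order, which would be far more predictable. The plan does not establish that reading. It is a further reason to state the within-block ratio to those who hold the list.

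**What to change.** 1. Delete the block size from the plan and record it in a restricted randomization document.
2. Use randomly varying, undisclosed blocks of similar length, for example 16, 20 and 24. Avoid short blocks.
3. Do not let the sizes be known to sum to 80 at a site. For example, let the list run past the 80th subject, so that the last order cannot be deduced.
4. Name a list holder who is independent of the operators, and state the blocking unit in the plan.
5. State whether a replaced subject's order is reused. Account for every subject whose order was disclosed, including those withdrawn or logged as screen failures afterwards. This also covers exits after disclosure, which need no prediction and which better blocking cannot prevent.

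The cost is a new list and a short edit, with no change to the planned sample size. The price is a slightly larger possible imbalance between orders at a site or at the interim analysis planned on completion of each site: four full blocks of 20 end exactly balanced, whereas a list stopped inside a block of 24 can be out by at most 24/2 = 12 subjects. The benefit should be described as removing the known certain slots, not as making orders harder to guess on average.

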6.2 Investigational Device(s) and Comparator(s)

Each subject will undergo back-to-back tandem colonoscopies, which could last approximately up to one (1) hour each. It is possible that procedures that have multiple therapeutic interventions may go beyond the expected time frames.

The Aer-O-Scope Colonoscope System will be compared to standard conventional colonoscopes that are normally used at the study sites (see Appendix 2 for the exact scope models). This study is intended to compare visualization properties of the currently used technologies; therefore, the standard colonoscope was chosen as the comparator.

During the course of this investigation, subjects will undergo the standard (split) bowel preparation used for colonoscopy at the clinic. This may include but may not be limited to one of the following medications:

- Moviprep
- Picolax
- Miralax
- Motilium
- Laxadine
- Golytely

During the course of this investigation, subjects will undergo the standard sedation given for colonoscopy. This may include but is not limited to the following medications:

- Biatryl/Fentanyl
- Dormicum/Medazolam
- Propofol

Clinical Investigational Plan			
Protocol ID	934CLD	Sponsor	GI View Ltd.
Revision	03	Investigational Device	Aer-O-Scope® Colonoscope System

During the course of this investigation, subjects who have findings during their colonoscopies will undergo polypectomies and/or biopsies and/or tattooing using standard therapeutic tools. This may include but is not limited to the following therapeutic tools and medications:

Biopsy forceps – both hot and cold

- Snare – both hot and cold
- Needle – for tattooing or injecting
- Saline solution
- Tattooing ink
- Epinephrine
- Argon plasma coagulation
- Cautery forceps/needles

The number of polyps detected during the second pass colonoscopy (that were not removed or tattooed during the first pass) will represent the overall number of missed polyps for the first colonoscopy. The number of detected polyps is defined as the number of polyps detected during colonoscopy. Each polyp removed (regardless of first or second pass colonoscopy) will be sent to histology as a singular specimen. Histology will determine if the lesion removed is an adenoma, hyperplastic polyp, serrated adenoma, cancer etc.

Patients with polyps ≥ 20 mm detected during 1st pass with conventional colonoscopy will be withdrawn from the study. Patients with polyps ≥ 20 mm detected during 1st pass with the Aer-O-Scope[®] will be tattooed for polyp resection during the 2nd pass with a conventional colonoscope.

Patients with polyps ≥ 20 mm that were missed during a 1st pass with a conventional colonoscope and detected with the Aer-O-Scope will be tattooed and undergo a 3rd pass with a conventional colonoscope for polypectomy/EMR (endoscopic mucosal resection).

Upon determination of polyp histology, the NMA will be calculated for each procedure. The NMA is defined as the number of adenomas detected during the second pass colonoscopy and confirmed histologically, that were not removed (or tattooed) during the first pass colonoscopy. The NMA will be calculated for both cohorts alike. The AMR will then be calculated for each cohort.

In the event pathology that is too large to remove or in a location preventing endoscopic removal is visualized during the course of any procedure, the pathology will be marked using tattooing. In the event a lesion is too large to remove during second pass colonoscopy with the Aer-O-Scope Colonoscope System but can be removed endoscopically with a conventional colonoscope, the pathology will be tattooed and the subject will undergo a third procedure with a conventional colonoscope using the same bowel prep and sedation, to remove the said pathology. Pathologies of this type will not be considered missed by the Aer-O-Scope.

The Aer-O-Scope Disposable Scanner is a single use disposable device. Each subject will undergo a colonoscopy with a single Aer-O-Scope Disposable Scanner (heretofore “scanner”). In the event of a technical malfunction, the scanner will be replaced with a new one. The expected number of Aer-O-Scope Disposable Scanners to be used is 310 but more may be used in the event of device malfunction. Each subject will undergo a conventional colonoscopy with a conventional colonoscope. The conventional colonoscope is a reusable device that undergoes high level disinfection / reprocessing between procedures. Each clinic generally uses three (3) scopes per procedure room. One (1) scope in use, another awaiting the next procedure and the third in reprocessing. Three (3) sites will be participating in this clinical investigation; therefore, the number of conventional colonoscopes to be used is expected to be 9; however, more or less may be used according to the sites’ standard operational procedures.

Disposable and reusable therapeutic instruments will be used as needed.

An interim analysis will be performed upon completion of each study site.

Clinical Investigational Plan			
Protocol ID	934CLD	Sponsor	GI View Ltd.
Revision	03	Investigational Device	Aer-O-Scope® Colonoscope System

6.3 Subjects

Subject Selection	
Inclusion Criteria:
 
 1. Subject is indicated for screening, diagnostic (minor complaints such as rectal bleeding or minor abdominal pain) or surveillance colonoscopy 2. Subject willing to undergo tandem colonoscopies with Aer-O-Scope Colonoscope and a conventional colonoscope (including a single colon preparation bowel cleansing) 3. Subject between the ages of 45 and 75 (patients between the ages of 45 and 50 must have a family history of a first degree relative with onset of colon cancer before the age of 60). 4. Subject is able to understand and willing to sign informed consent form 
Exclusion Criteria:
 
 1. Personal history of colorectal neoplasia including familial adenomatous polyposis or hereditary nonpolyposis, colon cancer (HNPCC). 2. Diagnosis of active (flaring) inflammatory bowel disease (active ulcerative colitis or Crohn's colitis), bowel obstruction, or acute diverticulitis, or known severe diverticulosis, fecal incontinence or any known large-bowel disease that would require a predetermined therapeutic colonoscopy (non-screening, non-diagnostic or non-surveillance cases) 3. Severe gastrointestinal tract-related symptoms, or complaints, suggesting performance of a pre-determined therapeutic colonoscopy (non-screening, non-diagnostic or non-surveillance cases) 4. History of colonic resection 5. Clinically significant cardiovascular or pulmonary disease 6. Cancer or other life threatening disease or significant chronic condition that puts the subject at risk. 7. Blood-clotting disorders and/or current anticoagulant therapy (Subjects taking up to 100mg aspirin for prophylactic treatment are acceptable for this study) 8. Pregnancy 9. Previous radiation therapy to the abdomen 10. Morbid Obesity (BMI > 40 kg/m²) 11. Drug abuse or alcoholism 12. Subject is bed-ridden and/or unable to adequately communicate 13. Subject is under custodial care 14. Subject has a history of psychiatric disorders which would prevent compliance with study instructions 15. Participation in a clinical study within the previous 30 days
--------------------------	--

Withdrawal	Subjects will be removed from the study whenever it is necessary to safeguard their welfare. Non-compliance with the protocol or occurrence of serious adverse events may also necessitate discontinuation from the
-------------------	---

Clinical Investigational Plan

Protocol ID	934CLD	Sponsor	GI View Ltd.
Revision	03	Investigational Device	Aer-O-Scope® Colonoscope System

	
study. When a patient is removed from the study, a final physical examination must be performed. Subjects removed from the study because of an adverse event will be followed-up until the adverse event has resolved.
 
Additional reasons for removing a patient from the study:
 
 1 Subjects who express a desire to withdraw from the study. 2 Any medical condition that, in the opinion of the investigator, warrants discontinuation from the study for the safety of the patient. 3 Poor colonic bowel cleansing that prevents proper visualization and intubation of the colon. 4 A large (≥20mm) polyp removal during first pass colonoscopy with a conventional colonoscope 5 Use of clips during first pass colonoscopy with a conventional colonoscope
Point of Enrollment	
Subjects will meet with the physician or physician appointed representative (such as a clinical coordinator) and be given ample opportunity to read and review the provided informed consent form and will be asked to sign prior to the beginning the bowel cleansing regimen. Subjects will be given the opportunity to ask the physicians questions prior to signing the informed consent. Subjects unable to sign prior to the day of procedure will be asked to sign the patient informed consent prior to entering the procedure room. A signed copy of the form will be provided for each patient.

Duration	
This multi-center, multi-national study is expected to last no longer than twelve (12) months. Each subject will be enrolled, undergo Aer-O-Scope Colonoscopy and conventional colonoscopy and be followed 24-48 hours via telephone post procedure. Subjects undergoing therapeutic interventions will be followed until the final histological results and only then will be terminated from the study.

Number of Subjects	
This study will include a total of 310 subjects in three (3) sites. Each site will study up to between 100 and 110 subjects (depending on the number of sub-investigators undergoing training). Subjects will be enrolled over a three (3) month period at each site and will undergo procedures over a three (3) month period at each site.

